- **Follow-Up Visit 1 (FU1: Day 14)**
- **Follow-Up Visit 2 (FU2: Day 28)**

If any of the dose escalation stopping criteria have occurred in Part A or Part B, the SRC will make a final recommendation for dose escalation to the next cohort.

- **NOTE:** The dose escalation decision through the study will not be made until the following:
 - (1) All study participants in a given cohort have been enrolled,
 - (2) All such participants have completed Treatment Visit 5 (Day 7) (for SAD-Part A) and Treatment Visit 9 (Day 9) (for MAD-Part B) of the study or withdrawn from the study, whichever occurs first,
 - (3) The SRC will review the available safety data and recommend further dose escalation.

[figure not shown]
Additionally, dose escalation stopping criteria are defined per the below:

- a. Death in any participant in which the cause of death is judged to be possibly, probably or definitely related to MBS-COV.
- b. The occurrence in any participant of a severe local application site reaction (Grade 3 which doesn't resolve or recurs, or Grade 4) that is judged to be possibly, probably or definitely related to MBS-COV.
- c. The occurrence in any participant of a SAE whose causal relationship to MBS-COV is judged to be probably, possibly, or definitely related to MBS-COV.
- d. The occurrence, in two or more participants of Grade 3 AE or laboratory abnormalities, judged to be probably, possibly, or definitely related to MBS-COV.

- e. The occurrence of two of the same AE or laboratory abnormality \geq Grade 3 judged to be probably, possibly, or definitely related to receipt of MBS-COV
- f. The occurrence, in one or more participants of Grade 4 AE or laboratory abnormalities, judged to be probably, possibly, or definitely related to receipt of MBS-COV.
- g. Any pattern of significant symptoms, physical findings, or laboratory abnormalities that, although individually minor, collectively represent a safety concern in the opinion of the investigator and are judged by the SRC to be at least possibly related to MBS-COV.
- h. PK exposure limits of mean AUC of 385.6 h*ng/mL or C_{max} of 141.8 ng/mL for one cohort, whichever comes first.(Single dose: AUC of 386.9 h*ng/mL or C_{max} of 91.7 ng/mL).

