5.2.1. Participant Discontinuation

The Investigator can discontinue a participant at any time if in their clinical judgment considers to be medically necessary. Investigators considering discontinuing study treatment should contact the medical monitor prior to such discontinuation. Participants who have study treatment discontinued will continue to be followed, per protocol, whenever possible. Participants who have study treatment discontinued due to a serious adverse event will be followed until resolution or stabilization of the event as described in [Section 9.4.1](#) (SAE Follow-Up).

In addition, participants will be discontinued from the study in the following conditions:

- Withdrawal of consent.
- The participant has an AE and is unsuitable for the study as judged by the Investigator.
- The participant experiences events which significantly affect safety, tolerability, or PK profile of the drug, and is unsuitable for the study as judged by the Investigator.
- Participants have poor compliance or major protocol deviations occur is unsuitable for the study as judged by the investigator.
- The Investigator no longer believes participation is in the best interest of the participant.

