5.3. STUDY STOPPING CRITERIA

Upon occurrence of any of the following events, data will be reviewed by the Medical Monitor and the Lead Principal Investigator.

1. A significant unexpected AE occurs during the study, and the Investigator considers that the study should be terminated.
2. The study shall be terminated due to major violations of the clinical study protocol, GCP, or relevant regulations during the study.
3. The Sponsor requests termination under the premise of fully protecting the rights and safety of the participants (for financial reasons, management reasons, etc.).
4. The regulatory authority or Ethics Committee elects to terminate the study for certain reason.

In case the above listed event(s) occurred, participant accrual will be suspended pending further review and the FDA and other global regulatory authority will be notified. The study will be stopped if any of these stopping criteria are met unless, after reviewing the safety events of interest, the medical monitor and Sponsor, agree to allow the study to proceed. The FDA and other global regulatory authority will be consulted for any protocol amendment before restarting the study if a stopping rule is met.

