8.5. BLINDING AND PREVENTION OF BIAS

8.6. INTERIM ANALYSIS

There is no efficacy interim analysis planned for this study; however, the safety data from all participants of each completed cohort will be reviewed by the SRC prior to enrolment of further participants or dose escalation.

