9.2.3. Event Causality Assessment

AEs will be assigned a relationship (causality) to the study treatment. The Investigator will be responsible for determining the relationship between an AE and the study treatment. The type of event, organ system affected, and timing of onset of the event will be factors in assessing the likelihood that an AE is related to the study treatment. Relationship of AEs to study treatment will be classified as follows:

- 1. Definitely related:** This category applies to those AEs that the Investigator feels are incontrovertibly related to the study treatment. An AE may be assigned an attribution of definitely related if or when it meets all of the following criteria: (1) it follows a reasonable temporal sequence from administration of the study treatment; (2) it could not be reasonably explained by the known characteristics of the participant's clinical state, environmental or toxic factors, or other modes of therapy administered to the participant; (3) it follows a known response pattern to treatment with the study treatment.
- 2. Probably related:** This category applies to those AEs which, after careful medical consideration at the time they are evaluated, are felt with a high degree of certainty to be related to the study treatment. An AE may be considered probable if or when (must have three): (1) it follows a reasonable temporal sequence from administration of the study treatment. (2) It could not readily have been produced by participant's clinical state, environmental or toxic factors, or other therapies administered to the participant. (3) Disappears or is decreased upon discontinuation of the study treatment. (4) It follows a known response pattern to treatment with the study treatment.
- 3. Possibly related:** This category applies to those AEs which, after careful medical consideration at the time they are evaluated, are judged unlikely but cannot be ruled out with certainty to the study treatment. An AE may be considered possible if or when (must have two): (1) it follows a reasonable temporal sequence from administration of the study treatment. (2) It could not readily have been produced by participant's clinical state, environmental or toxic factors, or other therapies administered to the participant. (3) Disappears or is decreased upon discontinuation of the study treatment. (4) It follows a known response pattern to treatment with the study treatment.

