3.1. Part A: SAD phase

Part A includes 3 dose-escalation cohorts (0.3 mg/kg, 0.6 mg/kg, 1.2 mg/kg MBS-COV or placebo). Each cohort will include 8 participants (6 active and 2 placebo) per below table:

| Cohort | MBS-COV Does Active:placebo | Frequency of Does |
|--------|--------------------------------|-----------------------|
| A1 | 0.3 mg/kg (6:2) | Single Administration |
| A2 | 0.6 mg/kg (6:2) | Single Administration |
| A3 | 1.2 mg/kg (6:2) | Single Administration |

From the perspective of safety, sentinel dosing will be used in each cohort, and the first 2 subjects in each cohort will be randomized 1:1 to MBS-COV or placebo. If the dose can be well tolerated for 48 hours after full administration per the study Safety Review Committee (SRC) consisting of the sponsor (designee), site Principle Investigator, and medical monitor, the remaining 6 subjects in the cohort may be randomized 5:1 to MBS-COV or placebo.

All participants will have a screening visit within 28 days of check-in (Day -1) to determine eligibility. Eligible participants will be admitted to the study center on study Day -1 at which point their eligibility to participate in the study will be confirmed. Only those participants who successfully complete the screening phase and meet the study eligibility criteria will proceed to be randomized to receive a single dose of MBS-COV or placebo in the morning of Day 1 at the assigned dose.

The decision for cohort (dose level) escalation to the higher dose levels will be made by the study SRC after safety review of available information 7-day post treatment period. The data from SAD phase will be reviewed for safety trends to start MAD phase.

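### In the visible text, a related death, severe local reaction, SAE or clinical Grade 4 event does not by itself pause same-dose dosing in the current cohort

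*Protocol*

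**What the plan says.** Protocol section 3.1, repeated in the synopsis, lists dose escalation stopping criteria a to h. The ones that matter here are related death (a), a severe local reaction (b), a related SAE (c) and a related Grade 4 event (f). The stated consequence is the same for all: if any of the "stopping criteria have occurred in Part A or Part B, the SRC will make a final recommendation for dose escalation to the next cohort". The NOTE in the same section puts the escalation decision after the whole cohort has been enrolled and has completed Day 7 (Part A) or Day 9 (Part B), or has withdrawn. Section 8.6 follows that timing: "the safety data from all participants of each completed cohort will be reviewed by the SRC prior to enrolment of further participants or dose escalation".

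Section 5.3 has its own list of four events. Its only AE item reads "A significant unexpected AE occurs during the study, and the Investigator considers that the study should be terminated". Once an item on that list occurs, "In case the above listed event(s) occurred, participant accrual will be suspended pending further review". The default outcome is strong: "The study will be stopped if any of these stopping criteria are met unless, after reviewing the safety events of interest". The exception that follows is a joint agreement, between Sponsor and medical monitor, to let it proceed. Section 5.3 does not mention section 3.1 or criteria a to h.

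Section 5.2.1 lets the Investigator discontinue any participant on clinical grounds. One of its listed conditions is "The participant has an AE and is unsuitable for the study as judged by the Investigator"; another is that participation is no longer in that person's interest. Section 9.4 requires SAEs to be reported within 24 hours of awareness.

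**The concern.** This is a first-in-human study in healthy volunteers, and section 1.6 puts the systemic safety margin at the top dose, 1.2 mg/kg, at 0.952. Cohort B2 plans that dose daily for a week. The sponsor has already named the events that should stop escalation, but the text ties them only to what happens at the next dose level. The people first exposed after a related death or SAE are those in the same cohort at the same dose, and for them section 3.1 states no consequence. Unless another section supplies one, their protection rests on someone choosing to act.

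**Working it through.** The plan gives no figure on this point, so the check is mainly a comparison of provisions. For each one the question is whether a related death, severe local reaction, SAE or clinical Grade 4 event, by itself, requires a pause in the current cohort.

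- **3.1, criteria a–c and f:** the event is named, but the consequence concerns the next cohort. No pause is stated.
- **3.1, NOTE (1)–(2):** these set the earliest time for the escalation decision. They do not forbid an earlier SRC meeting, and they do not require one.
- **8.6:** SRC review is tied to completed cohorts. No pause within a cohort.
- **5.3, item 1:** needs a significant unexpected AE and also the Investigator's opinion in favour of termination. Meeting (a) or (c) is not sufficient.
- **5.3, items 2–4:** major violations, a sponsor request, or a regulator or ethics committee decision. None is set off by a clinical event alone.
- **5.2.1:** reaches any participant, including those without an AE, but at discretion.
- **9.4:** a reporting duty with a 24-hour limit. Part B doses are also about 24 hours apart, so the next dose can fall due before the report does.
- **Part A sentinel step (3.1):** the remaining six participants wait until the first two have tolerated the dose for 48 hours. This is a real hold, but it covers only that pair. Part B describes no sentinel step.

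Criteria a–f already contain a relatedness assessment, and section 9.2.3 says "The Investigator will be responsible for determining the relationship between an AE and the study treatment". As written, holding the current cohort through 5.3 item 1 takes a further opinion, that the whole study should be terminated.

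Simple arithmetic shows what the wording leaves open.

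*Part B.* Inputs: 8 active participants and 7 daily doses per cohort (Table 3-2). Planned active doses: 8 × 7 = 56. Assumptions, not stated in the documents: all participants start together, the event follows the doses on day d in one active participant, that person stops, and nobody uses discretion. Doses left in the other seven active participants: 7 × (7 − d).

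- d = 1: 7 × 6 = 42; 42/56 = 75%
- d = 3: 7 × 4 = 28; 28/56 = 50%
- d = 6: 7 × 1 = 7; 7/56 = 12.5%

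*Part A after the sentinel pair.* Input: 5 active and 1 placebo (SAP 3.1). If dosing is one at a time and the first is an active participant with an event, 6 − 1 = 5 remain, of whom 5 − 1 = 4 are active. If all six are dosed the same morning, 0 remain. The spacing is not stated.

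**The case against.** The strongest reply is that the plan has several ways to stop, and that no competent site would keep dosing after a related death. Part B is inpatient to Day 9, with vital signs and ECG three times on each dosing day. SAEs go to the Safety Contact or Sponsor within 24 hours, with follow-up information to the medical monitor, so roles that sit on the SRC are in the reporting chain. Section 3.1 itself foresees SRC review if the study stops early for safety. Section 5.2.1 would let the Investigator withdraw every member of a cohort. All of this stands. It shows that a pause is possible and likely, but not that one is required.

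Three stronger readings are tempting and are not supported:

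- A reader might infer that the SRC cannot meet until the cohort is complete. The NOTE times only the escalation decision.
- A reader might infer that 5.3 lets Part B dosing continue during its review, because it suspends accrual. But 5.3 also makes stopping the default and speaks of restarting the study, which presupposes a halt. At most, its wording on Part B dosing during the review is unclear.
- A reader might take the dose counts as expected exposure. They require that nobody acts after a serious event in a supervised unit, and they carry no weight for how serious the point is.

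Figures 0-1 and 3-1 could not be seen, nor could any SRC charter or the Safety Management Plan cited in 9.4. A hold could be stated in any of them.

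**Conclusion.** The point holds as a gap in what the plan requires. In the visible text, outside the Part A sentinel step, criteria a–c and a related clinical Grade 4 event under f do not by themselves pause dosing at the same dose in the current cohort. The routes that could pause it depend on discretion or on a separate decision under 5.3. No size in terms of risk can be given. The illustration runs from 7 to 42 of 56 active doses in Part B for events on Day 6 back to Day 1, and from 0 to 5 participants in Part A, under the assumptions shown. Confidence is moderate because of the documents that were not available. The point is worth correcting because the sponsor has already named the triggers and the population is healthy volunteers.

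**What to change.** In section 3.1 and the synopsis, state that criteria a–c, or a related clinical Grade 4 event under f, immediately pause enrolment and further dosing in the affected cohort, including Part B courses in progress. The pause lasts until the SRC completes an expedited review and documents a decision to resume. Add that NOTE conditions (1)–(2) delay only the decision to escalate.

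Keep this as a cohort-level hold in 3.1. A bare cross-reference to 5.3 would not do the same job: it would bring in a study-wide stop by default and FDA notification, and would give the decision to proceed to the medical monitor and Sponsor instead of the SRC.

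Leave d, e, g, laboratory-only Grade 4 values and h to SRC judgement. The laboratory scale in Appendix 1 is tight (potassium above 5.6 mEq/L, or PT above 1.25 × ULN, is Grade 4), so automatic holds there would be a trade-off. Criterion h includes a cohort-mean exposure limit, which is a different kind of trigger.

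The cost is wording. No new body is needed: the SAP already describes the sentinel decision as made "per the study Safety Review Committee (SRC) consisting of the sponsor (designee), site Principle Investigator, and medical monitor". The real downside is that a pause may interrupt a 7-day course and lose some Day 7 PK profiles. The documents give no replacement rule, so a Part B cohort could end with fewer than 8 active Day 7 profiles.

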- g. Any pattern of significant symptoms, physical findings, or laboratory abnormalities that, although individually minor, collectively represent a safety concern in the opinion of the investigator and are judged by the SRC to be at least possibly related to MBS-COV.
- h. PK exposure limits of mean AUC of 385.6 h*ng/mL or C_{max} of 141.8 ng/mL for one cohort, whichever comes first.(Single dose: AUC of 386.9 h*ng/mL or C_{max} of 91.7 ng/mL)

The SRC will review the PK data (if applicable) and safety trends of available information 7-day post treatment period of Cohort A1 and A2 (or if study stops prematurely due to safety reasons), to start part B of the study. The starting dose of Part B will be determined by SRC.

Figure 0-1: Dose Escalation Schematic**Blood Sample Collection for the PK study:**

- SAD cohorts A1 to A3:** For the single dose on day 1, blood samples will be collected before dosing, and afterwards at 5 min (± 1 min), 15 min (± 2 min), 0.5 h (± 5 min), 1 h (± 5 min), 2 h (± 5 min), 4 h (± 5 min), 8 h (± 10 min), 10 h (± 10 min), 24 h (± 10 min) and 48 h (± 10 min) (Total 11 samples) after dosing.
- MAD cohort B1 and B2:** Blood samples will be collected on Day 1 and Day 7 before dosing, and afterwards at 5 min (± 1 min), 15min (± 2 min), 0.5 h (± 5 min), 1 h (± 5 min), 2 h (± 5 min), 4 h (± 5 min), 8 h (± 10 min), 10 h (± 10 min) on Day 1; and at 5 min (± 1 min), 15min (± 2 min), 0.5 h (± 5 min), 1 h (± 5 min), 2 h (± 5 min), 4 h (± 5 min), 8 h (± 10 min), 10 h (± 10 min), 24 h (± 10 min) and 48 h (± 10 min) after dosing on Day 7; and before dosing on Day 2 to Day 6 (Total 25 samples). The detailed study schedule and assessments in each visit are provided in [Section 4](#) of the protocol.

Blood Sample Collection for the immunogenicity study:

- Blood Sample will be collected on Day 1 before dosing, Day 14 and Day 28 for SAD and MAD cohorts, and the analysis will be performed when analytic method is well-established.

Study Duration:**Part A****SAD Phase:**

- Screening Period (For SAD Phase Only): Up to 28 days
- Treatment Period: 7 days
 - In-unit: 3 day
- Follow-Up Period: Up to 21 days
- Total Study Duration:** Up to 56 days

Part B**MAD Phase:**

- Screening Period: Up to 28 days

- Treatment Period: 9 days
 - In-unit: 9 days
- Follow-Up Period: Up to 19 days after EOT
- **Total Study Duration:** Up to 56 days

Eligibility Criteria

Inclusion Criteria:

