3. STUDY DESIGN

3.1. GENERAL SCHEMA

This is a Phase I, randomized, double-blind study designed to evaluate the safety, tolerability, and PK of inhaled MBS-COV in healthy adult participants in the part A and part B of the study. A total of 44 male and female healthy participants will be enrolled. All participants, after signing the Informed Consent Form (ICF), will be assessed during the screening phase. Only those participants who successfully complete the screening phase and meet the study eligibility criteria will be enrolled. MBS-COV will be administered via inhalation through a portable nebulizer.

Part A (SAD phase)

Part A is randomized, blinded study of a single ascending dose (SAD) phase to evaluate the safety, tolerability and PK of inhaled MBS-COV in healthy participants.

All participants will have a screening visit within 28 days of check-in (Day -1) to determine eligibility. Eligible participants will be admitted to the study center on study Day -1 at which point their eligibility to participate in the study will be confirmed. Only those participants who successfully complete the screening phase and meet the study eligibility criteria will proceed to be randomized to receive a single dose of MBS-COV or placebo in the morning of Day 1 at the assigned dose.

Participants will be assigned to one of up to three doses of MBS-COV (0.3 mg/kg, 0.6 mg/kg, 1.2 mg/kg) to be treated sequentially with increasing doses. Each cohort will include eight (8) participants (6 active and 2 placebo) per below table:

Table 3-1: SAD Phase Cohorts

Cohort		Number of Participants	MBS-COV Dose (mg/kg)	Frequency of Dose
SAD Phase	A1	6 (MBS-COV) +2 (placebo)	0.3	Single Administration
	A2	6 (MBS-COV) +2 (placebo)	0.6	Single Administration
	A3	6 (MBS-COV) +2 (placebo)	1.2	Single Administration

SAD phase will include a sentinel design in which two (2) participants at the given cohort dose be initially enrolled. If the dose can be well tolerated for 48 hours after full administration per site Principle Investigator's judgement, the remaining 6 participants will be enrolled to receive a single dose of MBS-COV at the same dose.

The decision for cohort (dose level) escalation to the higher dose levels will be made by the study SRC after safety review of available information 7-day post treatment period. The data from SAD phase will be reviewed for safety trends to start MAD phase.

Part B (MAD Phase)

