This is a randomized, double-blind, placebo-controlled study in approximately 20 healthy participants. Doses will be selected based on a comprehensive review of SAD data and estimates of the clinically efficacious dose.

The MAD Phase of the study consists of a screening period followed by multiple dose administrations of MBS-COV or placebo through a portable nebulizer once daily for 7 consecutive days (Day 1 to Day 7). Participants will be followed up for 21 days to assess post-treatment safety.

The decision for the escalation to the higher dose levels will be made by the study SRC after safety review of available information 7-day post treatment period. Each cohort will include ten participants (8 active and 2 placebo) per table below:

Table 3-2: MAD Phase Cohorts

Cohort		Number of Participants	MBS-COV Dose (mg/kg)	Dose
MAD Phase	B1	8 (MBS-COV) +2 (placebo)	0.6	Once daily for 7 days
	B2	8 (MBS-COV) +2 (placebo)	1.2	Once daily for 7 days

Study Visits:

- **Screening Visit (SV: Up to 28 Days prior to Day 1):** Consists of signing the ICF and study qualification based on evaluation of inclusion/exclusion criteria.
- **Treatment Visit 0 (T0: Day -1):** All participants continuing to meet eligibility criteria will be enrolled into the study and confined to research clinic until Day 2 for cohort A1 to A3 (SAD phase) and Day 9 for cohort B1 to B2 (MAD phase).
- **Treatment Visit 1: Baseline Visit (T1: Day 1):** The first assigned study treatment dose will be administered after completion of all study evaluations. Adverse events and changes in concomitant medications will be collected. Participants in Cohorts A1 to A3 will inhaled a single dose of MBS-COV or placebo through a portable nebulizer on Day 1. Participants in cohort B1 and B2 will receive doses of MBS-COV or placebo by through a portable nebulizer once daily for 7 consecutive days from Day 1 to Day 7.

Part A (SAD Phase)

- **Treatment Visit 2 (T2: Day 2)**
- **Treatment Visit 3 (T3: Day 3)**
- **Treatment Visit 4 (T4: Day 4)**
- **Treatment Visit 5 (End of Treatment) (T5: Day 7)**

- **Follow-Up Visit 1 (FU1: Day 14)**
- **Follow-Up Visit 2 (FU2: Day 28)**

Part B (MAD Phase)

- **Treatment Visit 2 (T2: Day 2)**
- **Treatment Visit 3 (T3: Day 3)**
- **Treatment Visit 4 (T4: Day 4)**
- **Treatment Visit 5 (T5: Day 5)**
- **Treatment Visit 6 (T6: Day 6)**
- **Treatment Visit 7 (T7: Day 7)**
- **Treatment Visit 8 (T8: Day 8)**
- **Treatment Visit 8 (End of Treatment) (T9: Day 9)**

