The SRC will review the PK data (if applicable) and safety trends of available information 7-day post treatment period of Cohort A1 and A2 (or if study stops prematurely due to safety reasons), to start part B of the study. The starting dose of Part B will be determined by SRC.

Figure 3-1: Dose Escalation Scheme

Blood Sample Collection for the PK study:

- SAD cohorts A1 to A3:** For the single dose on day 1, blood samples will be collected before dosing, and afterwards at 5 min (± 1 min), 15 min (± 2 min), 0.5 h (± 5 min), 1 h (± 5 min), 2 h (± 5 min), 4 h (± 5 min), 8 h (± 10 min), 10 h (± 10 min), 24 h (± 10 min) and 48 h (± 10 min) (Total 11 samples) after dosing.
- MAD cohort B1 and B2:** Blood samples will be collected on Day 1 and Day 7 before dosing, and afterwards at 5 min (± 1 min), 15min (± 2 min), 0.5 h (± 5 min), 1 h (± 5 min), 2 h (± 5 min), 4 h (± 5 min), 8 h (± 10 min), 10 h (± 10 min) on Day 1; and at 5 min (± 1 min), 15min (± 2 min), 0.5 h (± 5 min), 1 h (± 5 min), 2 h (± 5 min), 4 h (± 5 min), 8 h (± 10 min) on Day 7.

10 min), 10 h (\pm 10 min), 24 h (\pm 10 min) and 48 h (\pm 10 min) after dosing on Day 7; and before dosing on Day 2 to Day 6 (Total 25 samples). The detailed study schedule and assessments in each visit are provided in [Section 4](#) of the protocol.

Blood Sample Collection for the immunogenicity study:

- Blood Sample will be collected on Day 1 before dosing, Day 14 and Day 28 for SAD and MAD cohorts, and the analysis will be performed when analytic method is well-established.

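### PK stopping criterion h checks only the cohort already dosed; a projection to the next, doubled dose would be a cheap addition, chiefly at A2 to A3

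*Protocol*

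**What the plan says.** Criterion h, in the protocol synopsis and section 3.1, reads "PK exposure limits of mean AUC of 385.6 h*ng/mL or C_{max} of 141.8 ng/mL for one cohort, whichever comes first" and adds in brackets "Single dose: AUC of 386.9 h*ng/mL or C_{max} of 91.7 ng/mL". I take the bracketed pair as governing Part A and the main pair as governing Part B; the text does not label the main pair. The list that contains h comes into play once a criterion has been met, and the SRC then makes the final recommendation, so h is a trigger for review and not an automatic stop.

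The dose plan for Part A is: "Participants will be assigned to one of up to three doses of MBS-COV (0.3 mg/kg, 0.6 mg/kg, 1.2 mg/kg) to be treated sequentially". Part B has 0.6 and then 1.2 mg/kg once daily for 7 days.

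On what the SRC looks at:
- Section 3.1, NOTE (3), on escalation: "The SRC will review the available safety data and recommend further dose escalation".
- Section 8.6: "the safety data from all participants of each completed cohort will be reviewed by the SRC" before further enrolment or escalation.
- Section 3.1, on starting Part B after A1 and A2: "The SRC will review the PK data (if applicable) and safety trends".
- Section 3.1, on Part B doses: "Doses will be selected based on a comprehensive review of SAD data and estimates of the clinically efficacious dose".

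The Part A sentinel hold turns on tolerability: "If the dose can be well tolerated for 48 hours after full administration". SAP sections 4.4, 7.2.3 and 7.5 send all PK matters to a separate PK SAP, which is not among the documents.

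**The concern.** An exposure limit protects participants best when it is consulted before the dose that might breach it. Criterion h is the only numerical exposure criterion in this first-in-human study; criteria a to g rest on events or findings. Because the next dose is twice the current one, a cohort can sit well inside the limit while the next is expected beyond it. Applied to the letter, h would register this only after six more healthy volunteers (A3) or eight more (B2) had received active drug. The sentinel hold in Part A limits how many are exposed at once, but it assesses 48-hour tolerability and not plasma levels.

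The three steps differ. A2 to A3 matters most, being the first use of 1.2 mg/kg in Part A. B1 to B2 matters mainly if A3 PK is not yet available, which is possible because the start of Part B is tied to A1 and A2 only. At A1 to A2 there is a single dose level, so any projection rests wholly on assumed proportionality.

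**Working it through.** **Inputs from the documents.** Single-dose limits: AUC 386.9 h*ng/mL, Cmax 91.7 ng/mL. Main limits, read as multiple-dose: 385.6 and 141.8. Dose ratio at each within-part step: 0.6/0.3 = 1.2/0.6 = 2. Active participants per cohort: 6 in Part A, 8 in Part B.

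**Figures the plan states.** The limits have no derivation in the documents, so they cannot be reproduced. The nearest stated figure that can be is the systemic safety margin in protocol section 1.6: 87.9 × 0.1 × 0.13 / dose gives 3.809 at 0.3 mg/kg and 0.952 at 1.2 mg/kg, as stated. The same formula gives 1.90 at 0.6 mg/kg. The documents do not connect this margin to the plasma limits, so it is context only.

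**Crossing point.** If mean exposure varies as dose^b, the next cohort's expected mean is the current mean × 2^b. It reaches the limit when the current mean equals limit / 2^b. The exponent b is an assumption; b = 1 is dose-proportional.

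| b | Fraction of limit | A2 AUC (h*ng/mL) | A2 Cmax (ng/mL) |
|---|---|---|---|
| 0.6 | 66% | 255.3 | 60.5 |
| 0.8 | 57% | 222.2 | 52.7 |
| 1.0 | 50% | 193.5 | 45.9 |
| 1.2 | 44% | 168.4 | 39.9 |

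An A2 mean between the tabulated value and the full limit does not meet h, while A3 is expected above the limit. For B1 to B2 at b = 1 the crossing points are 385.6/2 = 192.8 h*ng/mL and 141.8/2 = 70.9 ng/mL.

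**Illustration.** Suppose the true A2 mean is 75% of the limit. The expected A3 mean is 0.75 × 2 = 150% of the limit at b = 1, and 0.75 × 2^0.6 = 114% at b = 0.6. I simulated arithmetic means of 6 lognormal values (400,000 cohorts); the CVs, exponents and true mean are all assumptions.

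| Quantity (true A2 mean 75% of limit) | CV 30% | CV 40% | CV 60% |
|---|---|---|---|
| A2 does not meet h, one metric near its limit | 0.99 | 0.97 | 0.91 |
| A3 observed mean above limit, b = 1.0 | 1.00 | 0.99 | 0.94 |
| same, b = 0.8 | 0.98 | 0.94 | 0.84 |
| same, b = 0.6 | 0.84 | 0.76 | 0.66 |

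Criterion h is met by AUC or Cmax. If both are at 75% of their limits, the chance that A2 does not meet h at CV 60% falls from 0.91 to 0.82–0.86 (log-scale correlation 0 to 0.8, assumed).

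**How often a projection check would fire.** The prompt is 2 × observed A2 mean above the limit. With a true A2 mean at 50% of the limit it fires about 45–48% of the time if one metric is near its limit, and about 55–73% if both are (CV 30–60%, correlation 0 to 0.8). If b were 0.8, that A2 mean would lead to an expected A3 mean of 0.5 × 2^0.8 = 87% of the limit, so those prompts would be unnecessary.

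**The case against.** The strongest reply is that passing h authorises nothing. Every step needs an affirmative SRC recommendation, the protocol speaks of up to three doses, and h supplies the number against which a committee can double a cohort mean in its head. Since h is itself a PK criterion, it implies that PK will be looked at. All of this stands. A reader might infer that the plan leaves the SRC unaware of the problem or lets A3 proceed automatically; the documents do not support that. What remains is that no available text asks for the comparison, and the escalation text names safety data without saying that PK results must be in hand.

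Second, the absence is judged without the PK SAP and the escalation figure, either of which might contain the check. That also stands, and it limits the point to the documents available.

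Third, the scenario is hypothetical. No predicted human exposure is given, and the simulation largely restates that twice 0.75 exceeds 1.

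Fourth, a reader might take the 0.952 margin as evidence that A3 would be unsafe or would breach the limit. It is not. Section 1.6 sets 10% hamster deposition against 100% human, the NOAEL is the highest dose tested, the section judges doses up to 1.2 mg/kg adequately supported, and nothing links the margin to the plasma limits.

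**Conclusion.** The point holds as an inexpensive improvement to a stated rule. It is not a contradiction or an error in the plan. As written, h tests a dosed cohort only. At A2 to A3, A2 means in roughly the upper half of the single-dose limit do not meet it while A3 is expected above the limit. The lower edge of that zone moves from 66% to 44% of the limit as the dose exponent goes from 0.6 to 1.2, so the gap exists at every exponent examined.

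The conclusion rests on exposure rising with dose about as a power function, and on the unseen PK SAP and figure not already containing the check. How likely A2 is to fall in this zone cannot be judged from the documents.

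**What to change.** Add to criterion h, in the synopsis and in section 3.1:

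> Cohort mean AUC and Cmax (active arm) will be available to the SRC before each escalation. The SRC will compare with the limits both the observed means and the means projected to the next planned dose (observed mean × dose ratio, using A3 and accumulation data for B1 to B2 where available). If either projection exceeds its limit, the SRC will hold, choose a lower dose, or record its reason for escalating.

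SAP section 3.1 places the site principal investigator on the SRC, so the cohort-level figures should be supplied in a way that protects the blind, for example by a preparer outside the blinded team. If the PK SAP already contains this check, a cross-reference in criterion h is enough.

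The cost is three sentences and a short table at up to three SRC meetings. In Part A the last PK sample (48 h, Day 3) falls four days before the Day 7 visit that gates escalation. In Part B it falls on the Day 9 gating visit itself, so B1 to B2 is where escalation is most likely to wait for assay results. Some prompts will prove unnecessary if PK is less than proportional, at the rates shown above; where the SRC still escalates, the price of such a prompt is a recorded reason.
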